### YMCA modified branching Exercise Protocol:

The subject will be familiarized with the cycle ergometer if they are not already. They will be properly positioned with an upright posture, proper bend in the knee for maximal leg extension and hands placed on the handle bars. The subject will have a few minutes to become comfortable and warm up before starting the protocol. The first stage of the protocol involves the subject pedaling at a steady state (~100rpm), at 100 watts or 150 kg / m / min for three minutes. As long as the subject reaches a steady state heart rate, defined as a heart rate that does not increase more than 5 beat per a minute in the last minute of the stage, they will move to the next stage. The next stage's intensity will depend on the difference between their warm up heart rate and the heart rate reached during the first stage. They will increase their Watts or kg/ m/ min as shown in Figure 1. Once the subject experiences symptoms the testing will stop. If the subject does not have an increase in symptoms and can reach 85% of their age- predicated heart rate, the testing will stop. Subject will remain on the cycle ergometer for a 2 minute recovery period before getting off.

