## **D. Design and Methods**

### **(1) Study Design**

Prospective, non-blinded, Interventional study

We plan to recruit up to 60 concussed patients, equally randomized to an intervention group who participate in the at home exercise program, or those who undergo the same testing but receive the standard of care given by their physician. Subjects will be recruited from Boston Children's Hospital Sports Medicine Clinic, The Micheli Center for Sports Injury Prevention as well as affiliated schools, clinics and sports organizations. The subjects and parents/guardians who voluntarily agree to participate will be scheduled for three visits. Upon the first visit, a research coordinator will explain the study and have the subject and parent/guardian sign the "Research Consent Form", approved by the Institutional Review Board of Boston Children's Hospital before participating in the study. Subjects will be required to complete three visits to The Micheli Center for Sports Injury Prevention or Spaulding Hospital in Cambridge for testing.

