## **(2) Patient Selection and Inclusion/Exclusion Criteria**

### **Inclusion**

- Male or females between 14-21 years of age
- Experienced a concussion within 14 days of testing, defined as a person who has had a traumatically induced physiological disruption of brain function, manifested by at least one of the following:
  - Any period of loss of consciousness;
  - Any loss of memory for events immediately before or after the accident;
  - Any alteration in mental state at the time of the accident (ie., feeling dazed, disoriented, or confused)
  - Symptoms of nausea, dizziness, fatigue, headache, or changes in sleep, cognition or, emotions following the accident
- Low or moderate cardiac risk according to American College of Sports Medicine (11)

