## **(3) Description of Study Treatments or Exposures/Predictors**

Concussion Symptoms will be monitored by the Post-Concussion Symptom Inventory (PCSI), Post-Concussion Symptom Score (PCSS), the abbreviated Concussion Symptom Inventory (CSI), and Visual analog scale (VAS)

Surveys: Dizziness Handicap Scale, Hospital Anxiety and Depression Scale (HADS), Patient Health Questionnaire (PHQ) will be completed before each testing visit.

Height and weight will be measured.

Heart rate, cerebral blood flow, and end-tidal CO2 will be recorded during a one hour session, before graded exercise test, during a graded exercise test on a cycle ergometer, and during 5 minutes of recovery. The branching exercise protocol (shown in Figure 1 below) based on the modified YMCA protocol will progressively increase exercise intensity up to 85% of age-predicted maximum heart rate. Exercise will be stopped at this point or if the volunteer becomes symptomatic.

Single/ Dual-Task Gait: Patients will be instrumented with three accelerometer devices, attached via elastic strap at L5, left, and right feet, which take less than one minute to place on the patient. The devices will be wirelessly connected to a laptop run by the study coordinator to obtain and save motion data. While wearing these devices, they will complete tasks in three different conditions:

- *Standing single-task:* patients will be seated and be asked to complete a mini-mental status examination, adapted from previous investigations and recommendations. It consists of spelling a five letter word backwards, serial subtraction of 6s or 7s, or reciting the months in reverse order. 8 trials will be completed.
- *Walking single-task:* patients will be instructed to walk down the hall at a length of 10m, turn around and return to the original starting point, with no obstruction or completion of other tasks. 8 trials will be completed.
- *Walking dual-task:* patients will be instructed to walk down the hall at a length of 10m, turn around and return to the original starting point, while completing a mental status examination. The examiner will ask the patient to spell a five letter word backwards, subtract by 6s or 7s from a number, or recite the months in reverse order. The examiner will say, "Ready, go" and the patient will begin walking while completing the mental task. 8 trials will be completed.

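### The first-stage ergometer load is given as 100 watts or 150 kg/m/min, but these differ about fourfold, so as statements of one load at least one figure is wrong

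*Combined protocol and SAP*

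**What the plan says.** The YMCA modified branching Exercise Protocol section, under D(3), describes a short warm-up and then a first stage pedalled at about 100 rpm "at 100 watts or 150 kg / m / min for three minutes". If heart rate is steady by the end of the stage, the participant moves on: "The next stage's intensity will depend on the difference between their warm up heart rate and the heart rate reached during the first stage". The section then says: "They will increase their Watts or kg/ m/ min as shown in Figure 1". No other visible part of the document restates the first-stage load, and Figure 1 is not reproduced in this copy.

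Section D(3) says the test "will progressively increase exercise intensity up to 85% of age-predicted maximum heart rate", and that it stops there or when the participant becomes symptomatic. Section D(5) has both arms take the graded test at visit 1 and repeat it at visits 2 and 3.

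**The concern.** The sentence gives one setting in two units, and the two numbers do not convert into each other. The later reference to Figure 1 uses the same pair of units, again joined by *or*. That suggests the word links equivalent units and does not offer a choice of two loads.

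Three things make this more than background text:

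- It is an instruction to be carried out at every graded test, in both arms.
- The heart-rate rise from warm-up to the end of the first stage decides the next stage, so the starting load feeds the branching.
- At visit 1 it is the initial load for adolescents and young adults who have, in the words of the inclusion criteria, "Experienced a concussion within 14 days of testing".

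Staff who set the ergometer in watts and staff who set it in kgf·m/min could start participants about 75 W apart while each followed the sentence. The document does not say which units the ergometers use, so this is a possibility and not an observed inconsistency.

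**Working it through.** **Inputs**

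- First-stage load: 100 W, and 150 in the second unit (YMCA modified branching Exercise Protocol section).
- Stage length three minutes (180 s) and cadence about 100 rpm (same section).
- Number of participants: "We plan to recruit up to 60 concussed patients" (D(1) Study Design).
- Number of visits: "Subjects will be required to complete three visits" (D(1) Study Design).
- Standard gravity, 9.80665 m/s². This is a physical constant and is not in the document.
- Assumption: the printed kg/m/min means kgf·m/min, because as printed it is not a unit of power.

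**Conversion**

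1. 1 kgf·m/min = 9.80665 / 60 = 0.16344 W.
2. 150 kgf·m/min = 150 × 0.16344 = 24.52 W.
3. 100 W = 100 / 0.16344 = 611.8 kgf·m/min.
4. Ratio: 100 / 24.52 = 4.08. Gap: 100 − 24.52 = 75.5 W.

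Neither stated figure can be reproduced from the other.

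**Could another unit or a rounded factor explain it?**

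| Reading of 150 | Watts |
|---|---|
| kgf·m/min, rounded factor (150 / 6) | 25 |
| N·m/min (150 / 60) | 2.5 |
| ft-lb/min | 3.4 |
| kgf·m/s (150 × 9.80665) | 1471 |

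None gives 100 W.

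**Could rounding explain it?** Suppose 150 was rounded to the nearest 50 and 100 W to the nearest 10; both widths are assumptions.

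- 125 × 0.16344 = 20.43 W and 175 × 0.16344 = 28.60 W.
- Smallest ratio: 95 / 28.60 = 3.32. Largest ratio: 105 / 20.43 = 5.14.

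The mismatch survives.

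**Could cadence explain it?** Both figures are already work rates, so cadence does not enter the conversion. As a check, 100 rpm is 10.472 rad/s:

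- Torque for 100 W: 100 / 10.472 = 9.55 N·m.
- Torque for 24.52 W: 24.52 / 10.472 = 2.34 N·m.

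At the lower torque, reaching 100 W would take 100 × 4.08 = 408 rpm.

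**Size in use**

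- Work over the stage: 100 × 180 = 18.0 kJ, against 24.52 × 180 = 4.41 kJ.
- Planned tests that use the setting: up to 60 × 3 = 180. This counts where the setting applies, not tests shown to be affected.

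**The case against.** The arithmetic is not in dispute. The case against giving the point weight runs as follows.

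- **The two values are never said to be equal.** They might be alternative starting loads. This is possible but is the weaker reading: the text gives no rule for choosing between them, and the same section uses *or* between these units when it refers to Figure 1. If two loads were intended, the missing rule would itself need to be added.
- **Figure 1 may settle the matter.** This stands in part. The figure cannot be seen here, and it may give staff a clear starting load. A single starting load there would agree with at most one of the two numbers, so the sentence would still need correcting. If the figure set out two alternative starting loads, the numbers could coexist, but the sentence should then say when each applies. The text cites Figure 1 only for the increase after the first stage.
- **Nothing downstream depends on the wattage.** This largely stands. The test ends at symptoms or a heart-rate limit, not at a set load. The home target comes from resting heart rate and the maximum heart rate reached in testing. The model in Section H has no workload term, and the power statement in Section I does not use one. Both arms take the same test.
- **The unit is readily understood.** Agreed. Its notation alone would be an editorial remark. The substance is the fourfold difference in the numbers.

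**Conclusion.** The concern holds, as a minor error in the specification of the exercise test. As two statements of one load, 100 W and 150 kgf·m/min are 4.08-fold apart (100 W against 24.5 W), and at least one is wrong. The visible text does not show which figure is wrong or how the error arose.

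The conclusion rests on two readings: that the printed unit means kgf·m/min, and that *or* joins equivalent units. Confidence in the arithmetic is high. The practical consequence is limited by the warm-up, the ECG and blood-pressure monitoring, and stopping at symptoms or at 85% of age-predicted maximum heart rate. No effect on the between-arm comparison, the power statement or the home training target is shown. What remains is an ambiguous starting load that bears on participant safety at visit 1 and on the consistency of the test across participants and visits.

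**What to change.** State a single first-stage load, as the investigators intend it, with a correct conversion:

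- about 25 W = 150 kgf·m/min, or
- 100 W = about 612 kgf·m/min.

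Write the unit as kgf·m/min wherever it appears in the section, and confirm that Figure 1 shows the same starting load and unit. If two starting loads really are intended, say so and give the rule for choosing between them.

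The cost is a one-line protocol correction and a check of one figure. It adds no visits, procedures or data fields.

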**Figure 1: Modified sub-maximal exercise protocol**

#### **(4) Definition of Primary and Secondary Outcomes/Endpoints**

- Primary: blood oxygenation level in the prefrontal cortex before and after the administration of the exercise protocol.
- Secondary: the proportion of participants who continue to experience symptoms after the 8-week exercise intervention and the potential confounding variables that contributes to this risk of persistent symptoms.

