## **A. Specific Aims/Objectives**

1. To observe how concussion affects cerebrovascular function and symptoms among adolescents.
2. To investigate the effect of a sub-maximal exercise protocol on cerebrovascular function and concussion symptoms in adolescents who have recently sustained a concussion.

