***Schedule:***

Recruitment: Potential concussed subjects will be recruited from the sports medicine clinic at Boston Children's Hospital by a research staff member. If the subject is eligible and interested in participating they will schedule study visit 1 with the research staff member.

Study Visit 1 (time of enrollment):

Subjects will come to The Micheli Center for Sports Injury Prevention or Spaulding Hospital in Cambridge for a two hour visit. Once they give consent we can schedule a time for testing.

Subjects will be measured for height and weight. Subjects will complete a short medical history questionnaire, which includes the DHS, HADS, PHQ and a PCSI/ PSCC. Subjects will then be fitted for a Polar Wrist Unit and Heart Rate Monitor. During this time, they will also have a standard 5-lead ECG placed by a trained research member. Additionally, a research member will attach a blood pressure cuff to their non-dominant arm and to their middle finger (for photoplethysmographic measurements) and set up to the TCD and NIRS system. Both the usual care group and intervention group will complete this part of the study.

The first part of the study procedure involves supine rest, performing mental tasks, CO2 rebreathing, and resistance breathing to induce small periodic oscillations in arterial pressure. For resistance breathing, volunteers will breathe through a mouthpiece attached to a standard impedance threshold device made from latex-free PVC (PowerBreathe) set-up to moderate breathing resistance (10-20 cmH2O). There are no risks associated with mental or physical tasks (N-Back and finger tapping tasks) or resistance breathing. The CO2 re-breathing may cause slight lightheadedness in some people; however, this can be reversed almost immediately by switching them back to room air. Both usual care and intervention groups will complete this part of the study.

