The second part of the procedure involves the branching graded exercise test. Subjects will still be monitored using a standard 5-lead ECG and blood pressure measured by oscillometric blood pressure cuff. Throughout the graded exercise test cerebral blood flow will be monitored via TCD or NIRS. The subjects will also be connected to the metabolic cart to measure VO2. The exercise test will continue until the subject reports an increase in symptoms, using the abbreviated concussion symptom inventory or to 85% of their age-predicted maximum heart rate determined by the 5-lead ECG. The subject will be taken off the bike and cool down. Measurements will be taken for an additional five minutes. Both the usual care and intervention group will complete this part of the study.

After completion of testing, the subject will have the ECG, blood pressure cuff, metabolic cart, TCD and NIRS system removed. They will be monitored by a trained professional until symptoms ease or subject's heart rate and blood pressure has returned to resting values.

The final part of the procedure includes the single/ dual-task gait evaluation and VOMS.

Weeks 1-4 (at-home exercise):

Subjects in the intervention group will be advised to participate in aerobic exercise five days a week. This includes walking, biking, jogging and running. While participating in these activities, they will be wearing their Polar Wrist Unit and Heart Rate Monitor to help subjects track their exercise intensity. They will exercise for 20 minutes five times a week at 80% of their heart rate reverse, determined by their resting heart rate and maximum heart rate reached during exercise testing.

Usual care subjects will follow their physician's instructions for exercise and rest. They will also wear the Polar Wrist Unit and Heart Rate Monitor to track their exercise intensity, but will not receive a heart rate specific exercise recommendation.

Study Visit 2 (approximately 4 weeks post-enrollment):

All participants will participate in this visit. Subjects will undergo the same procedures as visit one, including the DHS, HADS, PHQ, PCSI/ PCSS, supine rest, graded exercise test, VOMS and

single/dual- task gait. At this time, the target heart rate for exercise will be adjusted to a new symptom limited heart rate for all participants who are still symptomatic based on the same procedure.

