## **H. Data Analysis Plan**

This protocol seeks to elucidate the relationship between regional brain blood flow and CO2 during exercise in individuals who have experienced a mild TBI, and to assess the effect of a standardized exercise protocol on cerebral blood flow.

Total hemoglobin concentration in the pre-frontal cortex will be calculated as the sum of oxygenated and deoxygenated hemoglobin (as measured by NIRS) and will serve as a surrogate for regional cerebral blood flow. The brain blood flow and end-tidal CO2 data will be aligned in time. The linear relationship between the two time series will be determined and compared across injury duration and symptom severity. We will use a linear mixed effect model akin to a multiple linear regression model where regional cerebral blood flow is used as the dependent variable, end-tidal CO2 is the independent variable, and symptom duration and amount of exercise are covariates.

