## **I. Statistical Power and Sample Considerations**

To estimate the sample size required to achieve our aims, we used R-language statistical software using a p-value cutoff of 0.05 and minimum statistical power of 0.8. To achieve our specific aim, we will compare the relation between regional blood flow and CO2 responses to a branching exercise protocol, while accounting for injury duration. Given this analysis plan, we estimated that obtaining data from 60 individuals will allow us to detect any relation with an R^2 of 0.31 or higher.

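### The primary endpoint does not identify one comparison, and as labelled it can be met by an acute response to the graded cycle test that does not use the randomisation

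*Combined protocol and SAP*

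**What the plan says.** Section D(4) states: "Primary: blood oxygenation level in the prefrontal cortex before and after the administration of the exercise protocol". The secondary endpoint beside it refers to persistent symptoms after the 8-week intervention. The primary gives no week.

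The term exercise protocol is used in two ways:

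- **The graded cycle test.** Section D(3) describes this test under the heading "YMCA modified branching Exercise Protocol". The Figure 1 caption, just above the endpoint, is "Modified sub-maximal exercise protocol". Section I also calls the test the branching exercise protocol.
- **Possibly the assigned treatment.** Aim 2 is "To investigate the effect of a sub-maximal exercise protocol on cerebrovascular function and concussion symptoms", and Section H sets out "to assess the effect of a standardized exercise protocol on cerebral blood flow". Section D(1), where the randomisation is described, calls the treatment an at-home exercise program instead.

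Under the D(5) Schedule both arms do the graded test at Visit 1. For Visit 2 (about week 4) and Visit 3 (week 8) the instruction is "Subjects will undergo the same procedures as visit one". Each session has several recording conditions: "The first part of the study procedure involves supine rest, performing mental tasks", then CO2 rebreathing and resistance breathing, then the graded test and five minutes of recovery.

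Section H models total haemoglobin on end-tidal CO2, with symptom duration and amount of exercise as covariates. Section I sizes the study "using a p-value cutoff of 0.05" and power of 0.8 for a relation between blood flow and CO2. No testing order, alpha allocation or exploratory label is given.

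**The concern.** A primary endpoint should tell the analyst which number decides the trial. This one leaves open whether the change is acute (minutes, around a cycle test) or longitudinal (weeks, over the home programme), which visit counts, and whether the arms are compared at all.

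The acute reading fits the document's labels best, and it is also the one furthest from the randomised question. Both arms cycle at every visit, so a before-to-after change pooled over arms describes how recently concussed adolescents respond to exercise. It cannot show what the home programme does. At Visit 1 the programme has not even begun. Such a change could nonetheless be reported as a positive primary result of a randomised interventional study.

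A second, smaller problem is that a choice made after the data are seen raises the chance of a false-positive primary result above the 0.05 used in Section I.

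**Working it through.** **1. The plan's own figure.** Section I says 60 individuals allow detection of R² of 0.31 or higher at 0.05 and power 0.8. For the overall regression F test, with noncentrality λ = n·R²/(1 − R²) and n = 60, the detectable R² is 0.119, 0.145, 0.163 and 0.178 with 1, 2, 3 and 4 predictors. The stated figure is not reproduced. The nearest match is a three-predictor model fitted within each arm, which needs 29 per arm, or 58 in total, but Section I does not describe that calculation. This is a separate matter. What counts here is that the figure concerns a flow–CO2 relation and so does not select or size any reading of the primary endpoint.

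**2. The readings.**

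| Reading | Time points | Uses the randomisation? |
|---|---|---|
| Acute change around the graded test, pooled over arms | Visits 1, 2, 3 | No |
| Change over the home programme, between arms | Week 4, week 8 | Yes |

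That makes 3 + 2 = 5 readings at a single recording condition.

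**3. Does another section choose?** Section H has no arm term and no visit term, and its covariate, amount of exercise, is not the assigned arm. Its variable is total haemoglobin (oxygenated plus deoxygenated), whereas D(4) says blood oxygenation level, so the variable is open too. Section I refers to responses to the branching test. None of these picks a row, a visit or a recording window.

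**4. False-positive rate if the choice is left open.** Assumptions: every null is true, each test is two-sided at 0.05, and the statistics are normal. The documents give neither sidedness nor correlations, so a range is shown. For k statistics with common correlation ρ,

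P(at least one |Z| > 1.96) = 1 − E[{Φ((1.96 − √ρ·G)/√(1 − ρ)) − Φ((−1.96 − √ρ·G)/√(1 − ρ))}^k], with G standard normal.

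- Week 4 and week 8 only (k = 2): 1 − 0.95² = 0.098 at ρ = 0; 0.091 at ρ = 0.5; 0.078 at ρ = 0.8.
- Three acute contrasts (k = 3): 1 − 0.95³ = 0.143; 0.125; 0.098.

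With arms of equal size and variance, a pooled mean and a between-arm difference are uncorrelated: Cov((A + B)/2, A − B) = (Var A − Var B)/2 = 0. The two groups of contrasts are therefore treated as independent blocks:

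- ρ = 0.5 within blocks: 1 − (1 − 0.0907)(1 − 0.1254) = 0.205
- ρ = 0.8 within blocks: 1 − (1 − 0.0781)(1 − 0.0982) = 0.169
- ρ = 0: 1 − 0.95⁵ = 0.226

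If the acute changes are also compared between arms, a simulation that models their overlap with the longitudinal contrasts gives about 0.20 to 0.21.

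**5. What 60 patients can detect for one between-arm contrast.** With 30 per arm, two-sided 0.05, 80% power and no dropout: (1.960 + 0.842) × √(2/30) = 0.72 SD.

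**The case against.** **The readings are not equally open.** The heading, the Figure 1 caption, Section I and the near match between Aim 2 and the caption all favour the graded test. If the home-programme reading is taken instead, the adjacent secondary endpoint points to week 8. This is fair, and five is a count of readings that fit the wording, not of equally likely ones. But the better-supported reading is the one that does not use the randomisation, so the objection strengthens the main harm. It also still leaves three visits.

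**No multiple testing is planned.** A reader might infer that the trial will test five contrasts at 0.05 each and so carries an error rate of about 0.20. The documents do not support that. The 0.05 appears only in the power section, and Section H describes one modelling approach. The rates above show what an open choice would permit; they do not describe a stated plan.

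**A pooled acute rise is not a type I error.** This stands. It would be a real effect answering another question, and no family-wise rate measures that harm. For false claims about home exercise over time, the relevant figure is the two-contrast one, about 0.09.

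**Counting every recording condition.** It is tempting to multiply the readings by rest, mental tasks, rebreathing and the other conditions. D(4) gives no basis for treating each as a candidate primary, so no such figure is offered. The unnamed window remains a gap.

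**Physiology, not a trial.** Section G says these studies are physiologic investigation. Section D(1) nevertheless calls the study interventional and randomises equally, and D(4) names a primary endpoint.

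**Conclusion.** The point holds: D(4) does not fix one primary comparison, and no other section does so. This goes beyond missing detail, because followed by its own labels the primary can be met without using the randomisation. The main cost is interpretive and has no error rate attached.

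The multiplicity cost is conditional on an analyst using the freedom. It is about 0.09 (0.08 to 0.10) for week 4 versus week 8, and about 0.20 (0.17 to 0.23) if all five readings were tried. Both rest on two-sided 0.05 tests, within-block correlation from 0 to 0.8 and, for the second, independent pooled and between-arm blocks.

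**What to change.** In D(4), name one contrast that uses the randomisation. One example is the between-arm difference in change from Visit 1 to Visit 3 (week 8) in one named NIRS variable, at supine rest before the graded test, tested two-sided at 0.05. Another single contrast would also serve if it is fixed before analysis. State whether the variable is oxygenation or the total haemoglobin of Section H.

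Then:

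- add arm, visit and their interaction to the Section H model;
- label the week-4 contrast, the acute changes and the other recording conditions secondary or exploratory;
- use graded exercise test and home exercise programme as separate terms in Section A, D(3), D(4), H and I;
- replace the Section I statement with what 60 patients can detect for this contrast (about 0.72 SD before any dropout).

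The example needs no new measurements or patients, since supine rest is recorded at Visit 1 and the procedures are repeated at Visit 3. The costs are that the other contrasts can no longer be reported as primary and that the stated power figure must go. Splitting alpha over five contrasts (0.01 each) would instead raise the detectable difference to (2.576 + 0.842) × √(2/30) = 0.88 SD, and would still leave pooled acute changes among the primaries.

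### The only specified model and the power statement contain no randomised arm, visit or before/after term, so as written they do not estimate the primary endpoint or use the randomisation

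*Combined protocol and SAP*

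**What the plan says.** - **Aim 2 (Section A):** "To investigate the effect of a sub-maximal exercise protocol on cerebrovascular function and concussion symptoms in adolescents".
- **Design (D(1)):** up to 60 patients, allocated equally to a home exercise programme or to their physician's standard care, with three visits.
- **Primary endpoint (D(4)):** "blood oxygenation level in the prefrontal cortex before and after the administration of the exercise protocol". The secondary endpoint is the proportion still symptomatic after the 8-week intervention.
- **Purpose in Section H:** to study the relation between regional flow and CO2 during exercise, and to "assess the effect of a standardized exercise protocol on cerebral blood flow".
- **Model in Section H:** a linear mixed model. The outcome is regional flow, represented by NIRS total haemoglobin ("Total hemoglobin concentration in the pre-frontal cortex will be calculated as the sum of oxygenated and deoxygenated hemoglobin"). The independent variable is end-tidal CO2, and "symptom duration and amount of exercise are covariates". The flow-CO2 relation is to be "compared across injury duration and symptom severity".
- **Power (Section I):** at 0.05 and 80% power, the comparison is of flow and CO2 "responses to a branching exercise protocol, while accounting for injury duration". The statement is that "obtaining data from 60 individuals will allow us to detect any relation" with an R² of at least 0.31.

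**The concern.** Sections A, D(1), D(4) and H's statement of purpose lead the reader to expect a before/after estimate and, since patients are randomised, a comparison between arms. The analysis that is specified answers a different question: how closely prefrontal flow tracks CO2, and whether that varies with injury duration and symptom severity.

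The nearest thing to an intervention term is amount of exercise. The D(5) schedule has usual-care patients wear the heart-rate monitor too and exercise as their physician advises. The covariate is therefore a quantity that arises after randomisation in both arms. Its coefficient is an observational dose association, not the randomised effect. Adding it to a model that did contain arm could absorb part of the arm effect.

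Two things are at stake. The primary contrast, measure, recording condition and visit would all be open to choice after the data are seen. And readers are not told what size of effect 60 patients can detect for the contrast that matters.

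**Working it through.** **1. Terms needed against terms present**

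| Reading of the exercise protocol | Support in the protocol | Term needed | In H? | In I? |
|---|---|---|---|---|
| Graded cycle test | D(3) heading for the test, Figure 1 title, Section I wording | Pre-test/post-test | No | No |
| Home programme | D(1) allocation; Section B's use of similar wording for treatment | Arm, with visit or baseline | No | No |

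The named right-hand-side terms in H are end-tidal CO2, symptom duration and amount of exercise: 0 of 3 is arm, visit or before/after. Section I names only injury duration as an adjustment. Both arms perform the graded test (D(5)), so the test does not separate the arms.

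**2. The plan's own figure**

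Inputs from Section I: N = 60, alpha 0.05, power 0.80, R² = 0.31. The number of predictors is not stated. I used the overall regression F test with noncentrality N·R²/(1 − R²).

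- Detectable R² at N = 60 is 0.12, 0.14 and 0.16 with 1, 2 and 3 predictors, and 0.20 with 6.
- Power at R² = 0.31 with 3 predictors is 99.3%.
- About 17 to 18 predictors would be needed for 0.31 to be the limit (0.305 and 0.314).

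So 0.31 is not reproduced with few predictors, and for its own target the statement errs on the safe side. The present point does not depend on this figure.

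**3. Detectable difference between arms**

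Inputs: 30 per arm (D(1), 60 ÷ 2), alpha 0.05, power 0.80 (Section I). Assumptions not in the documents: two-sided test; 20% loss as an alternative (30 × 0.8 = 24 per arm); correlation r between visits 1 and 3 of 0.3, 0.5 or 0.7; equal SD at both visits. Results are in SDs of the measure at one visit.

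Unadjusted, two-sample t: the normal approximation is (1.960 + 0.842) × √(2/30) = 0.723. The exact noncentral t gives d = 0.736 for 30 per arm and 0.826 for 24.

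Adjusted for visit 1: d × √(1 − r²). For example, 0.736 × √0.75 = 0.637.

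Change from visit 1 to visit 3: d × √(2(1 − r)). For example, 0.736 × √1.0 = 0.736.

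| Analysis | n per arm | r = 0.3 | r = 0.5 | r = 0.7 |
|---|---|---|---|---|
| Unadjusted | 30 | 0.74 | 0.74 | 0.74 |
| Unadjusted | 24 | 0.83 | 0.83 | 0.83 |
| Baseline-adjusted | 30 | 0.70 | 0.64 | 0.53 |
| Baseline-adjusted | 24 | 0.79 | 0.72 | 0.59 |
| Change | 30 | 0.87 | 0.74 | 0.57 |
| Change | 24 | 0.98 | 0.83 | 0.64 |

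Baseline adjustment detects smaller differences than the change analysis at every correlation shown.

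**4. Detectable within-person change (graded-test reading)**

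Paired t, two-sided 0.05, 80% power: 0.37 SD of the change with 60 pairs and 0.41 with 48 (60 × 0.8). These are SDs of the change score, so they are not on the same scale as step 3.

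**The case against.** **Aim 2 may be about the graded test.** This stands in part. Aim 2's wording closely matches the title of Figure 1, while D(1) and the secondary endpoint use other words for the home arm. On that reading H and I sit closer to the aims, because they model responses to that test. But the primary endpoint would then need a pre-test/post-test term, and none is given. It does limit one statement: that Aim 2 has no randomised test is true only if the home programme is meant.

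**A mixed model implies repeated measures.** It could accommodate visits, but no visit term or random-effect structure is stated, and symptom duration is neither a visit nor an arm term.

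**Section G calls the work physiologic investigation, not a clinical trial.** That sentence explains why there is no formal quality assurance programme. It does not withdraw the randomisation, the primary endpoint or H's stated purpose.

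**Any relation with R² of 0.31 might cover an arm effect.** For one binary predictor in equal arms, R² = 0.31 corresponds to d = 2 × √(0.31/0.69) = 1.34 SD. Section I does not present it as an arm contrast, and step 3 shows the actual limit is much smaller.

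**Two stronger readings are not supported.** A reader might infer that 60 patients are too few. The documents give no target arm difference or SD, so underpowering is not shown. A reader might also see a switch of outcome from oxygenation in D(4) to total haemoglobin in H. D(3) and H use them as measures of the same prefrontal flow, so this calls for one name, not a charge of switching.

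**Conclusion.** The point holds as a gap between endpoint and analysis. Followed literally, Sections H and I produce no estimate of the D(4) primary endpoint and no comparison of the randomised arms, on either meaning of the exercise protocol. This is more than missing detail, because the analysis that is specified addresses another question and adjusts for an exposure that arises after randomisation. The secondary symptom endpoint, which is the symptom half of Aim 2, has no specified arm comparison either.

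For scale, a baseline-adjusted arm comparison could detect 0.53 to 0.79 SD over the assumed correlations (0.3 to 0.7) and losses (none or 20%). The structural finding rests on the text alone; only these sizes rest on the assumptions. The plan should be changed, but nothing here shows the sample size to be inadequate.

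**What to change.** 1. **D(4).** State whether the graded test or the home programme is meant. Name one NIRS measure (oxygenation, total haemoglobin, or the slope of total haemoglobin on CO2), its recording condition and its visits. Use that definition unchanged in H and I.
2. **H, arm comparison.** Add: *The randomised arms will be compared, as randomised, on this measure at visit 3, adjusted for its visit 1 value.* Leave amount of exercise out of this model. Keep the flow-CO2 model as a separate stated analysis.
3. **H, if the graded test is meant.** Make the within-person pre-test to post-test contrast the primary estimate, naming its visit. Then compare that change between arms at visit 3, adjusted for the visit 1 change. The correlation to assume is then that between change scores, which may differ from the values above.
4. **H, symptoms.** Add an as-randomised comparison of the proportion still symptomatic at 8 weeks.
5. **I.** Give the detectable difference for the chosen contrast, with loss and correlation labelled as assumptions. Examples are 0.64 SD for the baseline-adjusted comparison (30 per arm, r = 0.5) and 0.37 SD of the change for the within-person contrast (60 pairs).

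**Cost.** Text and a little more analysis. NIRS is set up at visit 1 and the same procedures are repeated at visit 3 (D(5)). There is one exception: D(5) has flow monitored during the graded test by TCD or NIRS, not necessarily both. If the graded-test reading is chosen, the sponsor must also commit to recording NIRS through the test and recovery.
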